9.8 QUALITY CONTROL

All entries in the eCRF will be stored in a database. The structure of the database is based on the division into sections and entry fields defined in the eCRF. To improve and ensure data quality, data checks will be performed automatically in the eCRF directly on electronic entry at the study site.

Plausible value ranges for numerical data entries and logical data and list entries will be filed in the eCRF. The tests for consistency and completeness based on this will be performed during entry in the eCRF. The validity of the recorded data will therefore be ensured by the validations incorporated in the documentation system, which highlight incorrect or implausible entries to the data entry clerk/doctor.

If corrections are necessary after the data are saved, these will be documented in an audit trail.

For the further quality assurance of the documented patient observations, a sample-size based source data verification will be performed on about 30% of included patients. An additional inspection/quality assurance check of this NIS can be performed in case of any deviation.

9.9 LIMITATIONS OF THE RESEARCH METHODS

The generalization and consequently the external validity of the study results, may be limited by the participation in the study of only sites that prescribe Gi(l)otrif[®] on a regular basis to ensure sufficient patient recruitment. Patients treated by investigators with less experience might experience more side effects during their treatment with Gi(l)otrif[®].

Methodological efforts have been taken to minimize selection bias: these efforts include the recommendation to include consecutive patients meeting each of the inclusion criteria and none of the exclusion criteria. In addition, this possible selection bias may be limited by the retrospective aspect of the data collection, data that have been already collected at the time of the study. Linked to this aspect is then the limitation due to data availability. Indeed, no additional data will be collected for the study purpose. So if the data is not available in the patient files, then this will be considered as missing data.

In addition, to reduce error in data collection, a standard study eCRF will be used, ensuring a measure of consistency among the collectors.

Another limitation is coming from the diverse handling of data collection from deceased patients which is allowed without informed consent in some countries but not in all.

However, no country-based analyses will be done. Given the median overall survival (31.6 months in LUX-Lung 3) and that time from launch of Gi(l)otrif to data collection in the participating countries is shorter than the median overall survival (OS) the majority of the patients are expected to be alive.

External validity is provided by the global approach of this study and the broad inclusion criteria but limited to patients treated within the label and at the selected, experienced sites. Internal validity will be given by source data verification.

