[figure not shown]

Protocol for non-interventional studies based on existing data

Document Number:	c09038525-01
BI Study Number:	1200.270
BI Investigational Product:	Gi(l)otrif [®] (afatinib)
Title:	RealGiDo: Real-world data on Gi(l)otrif [®] dose adjustment in first-line treatment, TKI-naïve, advanced non-small cell lung cancer patients with EGFR activating mutations
Brief lay title:	Real World Data on Gi(l)otrif [®] dose adjustment
Protocol version identifier:	1.0
Date of last version of protocol:	01 March 2016
PASS:	No
EU PAS register number:	EU PAS register number not yet assigned as the study is not yet registered in the EU PAS Register. The study will be registered shortly before the start of data collection.
Active substance:	afatinib Antineoplastic agents, tyrosine kinase inhibitors ATC code: L01XE13
Medicinal product:	Gi(l)otrif [®] 50mg, 40mg, 30mg, 20mg tablet
Product reference:	20mg: EU/1/13/879/001, EU/1/13/879/002, EU/1/13/879/003 30mg: EU/1/13/879/004, EU/1/13/879/005, EU/1/13/879/006 40mg: EU/1/13/879/007, EU/1/13/879/008, EU/1/13/879/009 50mg: EU/1/13/879/010, EU/1/13/879/011, EU/1/13/879/012
Procedure number:	EMA/H/C/002280
Joint PASS:	No
Research question and objectives:	
Primary objective: To assess the effects of Gi(l)otrif[®] dose modification on the frequency and severity of adverse drug reactions, time on treatment and time to progression with Gi(l)otrif[®] in real-world setting and compare with data from Lux-Lung 3 trial in a descriptive manner.
 
Secondary objective: To obtain information on frequency and reasons for a modified starting dose of Gi(l)otrif[®] in real-world setting

Protocol for non-interventional studies based on existing data

BI Study Number 1200.270**c09038525-01**

Proprietary confidential information © 2016 Boehringer Ingelheim International GmbH or one or more of its affiliated companies

Countries of study:	Austria, Canada, France, Germany, Italy, Japan, Korea, Mexico, Poland, Singapore, Spain, Taiwan, US
Author:	 Phone:  Fax:  E-mail: 
Marketing authorisation holder:	Boehringer Ingelheim International GmbH [name] Germany
Date:	01 March 2016

Page 1 of 38**Proprietary confidential information****© 2016 Boehringer Ingelheim International GmbH or one or more of its affiliated companies. All rights reserved.**
This document may not - in full or in part - be passed on, reproduced, published or otherwise used without prior written permission

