	
 1. EGFR mutated (common mutations), TKI-naïve advanced NSCLC treated with Gi(1)otrif[®] as the first-line treatment for NSCLC within the approved label will be included 2. Patients treated within clinical trials are excluded 3. Patients still on treatment with Gi(1)otrif[®] will be excluded unless treatment period is ≥ 6 months
Variables:	
Primary outcomes:
 
Safety outcomes:
 
Percentage of subjects with adverse drug reactions by severity class
 
Effectiveness outcomes:
 
Time on treatment with Gi(1)otrif[®]
 
Time to progression with Gi(1)otrif[®]

Data sources:	NIS based on existing data from medical records of patients.
Study size:	At least 200 patients. ≥ 200 patients are planned based on feasibility aspects and assumptions.
Data analysis:	
Safety data will be analysed in a descriptive manner. Incidence and severity of adverse drug reactions will be summarized and displayed. For patients who have dose modifications, frequency and severity of the most common AEs pre- and post-dose modification will be summarized and displayed.
 
For effectiveness analysis, both time on treatment and time to progression will be estimated using Kaplan-Meier method, and the median along with two-sided 95% CI will be displayed (use the Greenwood's formula for estimation of standard errors). Log-rank test will be applied to compare between patients with and without dose modifications.

Milestones:	
Start of data collection in May 2016
 
End of data collection in December 2016
 
Final report of study results expected in March 2017

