7. RATIONALE AND BACKGROUND

The first marketing approval of afatinib was granted on 12 Jul 2013 in the USA (trade name Gilotrif[®]) for the indication of first-line treatment of patients with metastatic non-small cell lung cancer (NSCLC) whose tumors have epidermal growth factor receptor (EGFR) exon 19 deletions or exon 21 (L858R) substitution mutations as detected by an FDA-approved test. It was approved in the European Union on 25 Sep 2013 (trade name Giotrif[®]) as monotherapy indicated for the treatment of EGFR TKI-naïve adult patients with locally advanced or metastatic NSCLC with activating EGFR mutation(s). [REDACTED]

The approval of Giotrif[®] was based on the results observed in the pivotal trial LUX-Lung 3 study. The LUX-Lung 3 study investigated the efficacy of chemotherapy compared with afatinib, a selective, orally bioavailable ErbB family blocker that irreversibly blocks signaling from epidermal growth factor receptor (EGFR/ErbB1), human epidermal growth factor receptor 2 (HER2/ErbB2), and ErbB4 and has wide-spectrum preclinical activity against EGFR mutations. A total of 1,269 patients were screened, and 345 were randomly assigned to treatment (afatinib or chemotherapy). Median progression-free survival (PFS) was 11.1 months for afatinib and 6.9 months for chemotherapy (hazard ratio [HR], 0.58; 95% CI, 0.43 to 0.78; P=.001). Median PFS among those with exon 19 deletions and L858R EGFR mutations (n=308) was 13.6 months for afatinib and 6.9 months for chemotherapy (HR, 0.47; 95% CI, 0.34 to 0.65; P=.001). The most common treatment related adverse events were diarrhea, rash/acne, and stomatitis for afatinib and nausea, fatigue, and decreased appetite for chemotherapy. Patients reported outcomes (PROs) favored afatinib, with better control of cough, dyspnea, and pain ([P13-07382](#)).

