9.2.1 Selection of study population

Site selection:

Sites in countries with launch dates prior to 1st Jan 2015 and known to prescribe Gi(l)otrif[®] on a regular basis will be chosen. Asian and Non-Asian countries will be included.

Inclusion criteria:

All consecutive patients will be included if all the following criteria are present:

- Age \geq 18 years

Protocol for non-interventional studies based on existing data

BI Study Number 1200.270

c09038525-01

Proprietary confidential information © 2016 Boehringer Ingelheim International GmbH or one or more of its affiliated companies

- Patients with EGFR mutation (common mutations), TKI-naïve advanced NSCLC, treated with Gi(l)otrif[®] as the first-line treatment for NSCLC within the approved label
- Signed and dated written informed consent per regulations. (Exemption of a written informed consent for retrospective observational studies in some countries per local regulations and legal requirements.)

Exclusion criteria:

Patient won't be included if any of the following criteria is present:

- Any contraindication to Gi(l)otrif[®] as specified in label.
- Patients with uncommon mutations are excluded as uncommon mutations are not within label in all participating countries (e.g. USA).
- Patients still on treatment with Gi(l)otrif[®] will be excluded unless treatment period is ≥ 6 months.
- Patients treated with Gi(l)otrif[®] within an interventional trial.

A log of all patients included into the study will be maintained in the ISF at the investigational site.

Patients treated with Gi(l)otrif[®] in interventional trials are excluded to ensure the non-interventional setting of this study. The threshold of ≥ 6 months treatment with Gi(l)otrif[®] for patients being still on treatment was chosen to avoid early censoring and enable collection of mature data on ADRs and treatment duration. However, patients who stopped Gi(l)otrif[®] < 6 months will be included to avoid bias. All patients fulfilling inclusion and exclusion criteria from a site will be entered to avoid bias. The maximum of 15 patients per site was chosen to avoid bias by high proportion of patients coming from one site.

BI reserves the right to discontinue the study overall or at a particular study site at any time for the following reasons:

1. Failure to meet expected enrolment goals overall or at a particular study site.

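### Reassurance about missing deceased patients rests on launch timing that the protocol does not document, and no visible analysis would show the resulting upward bias in time to progression

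*Protocol*

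**What the plan says.** Protocol Section 9.9 names as a limitation the "diverse handling of data collection from deceased patients which is allowed without informed consent in some countries but not in all". It says that no analyses by country will be done. It then argues: "Given the median overall survival (31.6 months in LUX-Lung 3"), and because the time from launch "to data collection in the participating countries is shorter than the median overall survival (OS"), most patients should still be alive.

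The only launch information is the site-selection rule in Section 9.2.1: "Sites in countries with launch dates prior to 1st Jan 2015". The title page lists 13 countries: "Austria, Canada, France, Germany, Italy, Japan, Korea, Mexico, Poland, Singapore, Spain, Taiwan, US". Section 7 gives two approval dates: "The first marketing approval of afatinib was granted on 12 Jul 2013 in the USA" and "It was approved in the European Union on 25 Sep 2013". Section 6 sets data collection from 31 May to 31 December 2016.

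Section 10.1.1 asks sites to seek an exemption from written consent so that patients who cannot consent, including those who have died, are not lost. Where the exemption is refused, it requires consent from the patient or a legally accepted representative.

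Time on treatment and time to progression are primary outcomes (Section 9.3.2.1). They are to be set beside LUX-Lung 3 descriptively (Sections 8 and 9.7.1).

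**The concern.** The reassurance has two weak links.

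The first is factual. The dates the protocol does give point the other way for the US and for the six EU states on the list (Austria, France, Germany, Italy, Poland, Spain).

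The second is the inference. Even if most patients are alive, those who are not are no random subset. Death usually follows progression, so the patients most easily lost where consent cannot be waived are those with short time on treatment and early progression. Losing them would lengthen both effectiveness outcomes, and could also thin out early severe adverse drug reactions. Real-world results would then look better next to LUX-Lung 3 than they are.

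Consecutive inclusion does not protect against this. Signed consent is itself an inclusion criterion unless a local exemption applies (Section 9.2.1), and the site log covers only patients who were included. The number lost would therefore never be known.

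**Working it through.** **Step 1: the stated premise.** The plan's figure is a launch-to-collection time below 31.6 months. With no launch dates given, the only visible anchors are the approval dates and the latest launch that site selection allows. Months = days / (365.25/12).

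| From | To 31 May 2016 | To 31 Dec 2016 |
|---|---|---|
| US approval, 12 Jul 2013 | 1054 days = 34.6 | 1268 days = 41.7 |
| EU approval, 25 Sep 2013 | 979 days = 32.2 | 1193 days = 39.2 |
| Latest admissible launch, 31 Dec 2014 | 517 days = 17.0 | 731 days = 24.0 |

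As 31.6 months is about 962 days, the EU excess at the start of collection is only 979 − 962 = 17 days. The premise holds for launches after about 13 October 2013 if collection is at the start of the window, or after about 15 May 2014 if it is at the end. Counted to the protocol date (1 March 2016), the intervals are 31.6 months (US) and 29.2 months (EU).

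**Step 2: is a living majority still plausible?** Assume exponential survival with median 31.6 months and treatment starts spread evenly over T months from launch to collection. With λ = ln 2 / 31.6, the share alive is (1 − e^(−λT)) / (λT).

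- T = 32.2 to 41.7 (from the approval dates): 72% down to 66%.
- T = 17.0 to 24.0 (launch at the end of 2014): 84% down to 78%.

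So the conclusion about a majority can stand without the premise, because patients start over time.

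**Step 3: effect on time to progression.** All of the following are assumptions.

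- True time to progression is exponential with median 11.1 months, the overall LUX-Lung 3 afatinib PFS median in Section 7.
- Post-progression survival is exponential, scaled so that median overall survival is 31.6 months.
- Starts are uniform, from 35.7 or 20.5 months down to 6 months before collection. These are the intervals from EU approval and from 31 December 2014 to mid-September 2016, about the middle of the collection window.
- A given fraction of the patients dead at collection is lost.

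In this model death always follows progression, so counting death as an event changes nothing.

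| | Starts from 35.7 months | Starts from 20.5 months |
|---|---|---|
| Dead at collection | 30% | 16% |
| Median, none lost | 11.1 | 11.1 |
| Median, 25% of deceased lost | 11.9 | 11.7 |
| Median, 50% of deceased lost | 12.9 | 12.4 |

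Per 200 eligible patients, the number lost runs from 0.25 × 0.16 × 200 = 8 to 0.50 × 0.30 × 200 = 30.

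**Step 4: would the plan reveal it?** Section 9.9 rules out analyses by country. Item 10.4 of the ENCePP checklist (stratified analyses) is ticked No. The SAP's derivations of time on treatment and time to progression include no sensitivity analysis, and nothing visible records waiver status or patients not entered.

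**The case against.** **Approval is not launch.** A reader might infer from Step 1 that the protocol's sentence is false. The documents do not show that. Six of the 13 countries (Canada, Japan, Korea, Mexico, Singapore, Taiwan) have no visible date, a short gap after EU approval would restore the premise at the start of collection, and late-2014 launches satisfy it throughout. The sentence is unsupported, not disproved.

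**The protocol's conclusion survives.** Section 9.9 claims only that a majority should be alive, and Step 2 agrees. It does not say that the loss of deceased patients is negligible.

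**The problem is recognised and partly handled.** Section 10.1.1 asks for waivers for exactly this reason and allows consent through a representative. It would be wrong to infer that every deceased patient is lost wherever consent is required. What stands is that refusal is expressly provided for, and nothing then measures the result.

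**The size rests on unknown inputs.** No document gives the share of deceased patients who would be missed. The same model with every deceased patient lost gives medians of about 16 and 14 months, but Section 9.9 says some countries do allow their inclusion, so that scenario should not be used. At 200 patients the sampling range of an unbiased median is itself roughly 9 to 14 months, wider than the shifts shown. That gives the scale, but a larger sample would shrink sampling error and leave the bias. The model also leaves out patients who started within 6 months of collection and had already stopped, whom the study includes.

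**Some text is blacked out or not visible.** This affects Section 7 after the EU approval sentence, one contents entry after 9.7.1, and the SAP's planned tables. The absence of a check can be stated only for the visible text.

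**Conclusion.** The concern holds in a limited form. The launch-timing premise has no support in the protocol's own dates, and a living majority does not answer the bias in any case. Where waivers are refused, deceased patients may be missed, and the expected direction is longer time on treatment and time to progression.

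Under the Step 3 assumptions, the shift in median time to progression is about 0.6 to 1.8 months (11.1 to between 11.7 and 12.9) if 25% to 50% of the deceased are lost. That could colour a descriptive comparison with LUX-Lung 3. Whether it happens depends on waiver outcomes that were unknown when the protocol was written.

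Under-counting of severe adverse drug reactions is plausible but not quantified here. Nor is any effect shown on the comparison of patients with and without dose modification. This is a worthwhile, inexpensive improvement. Correcting the launch sentence alone would not achieve it.

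**What to change.** 1. Support the launch sentence in Section 9.9 with actual launch dates by country, or delete it.
2. Record for each site whether a waiver covering deceased patients applied.
3. Extend the site log to count otherwise eligible patients not entered because they were deceased or unreachable.
4. Repeat time on treatment, time to progression and adverse drug reaction severity in patients from waiver-covered sites, as a sensitivity analysis beside the full set.

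The cost is one site-level field, one count on the log and one extra set of tables, with no new clinical data. The waiver-covered subset will be smaller and less precise. It may also differ in country mix, so a difference from the full set would suggest survivor bias but not prove it. The count in item 3 helps to interpret it.

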9.10 OTHER ASPECTS

9.10.1 Data quality assurance

A quality assurance audit/inspection of this study may be conducted by the sponsor or sponsor's designees or by Institutional Review Board (IRB) / Independent Ethics Committee (IEC) or by regulatory authorities. The quality assurance auditor will have access to all medical records, the investigator's study-related files and correspondence, and the informed consent documentation of this NIS.

9.10.2 Records

eCRFs for individual patients will be provided by the sponsor (BI) via RDC system.

9.10.2.1 Source documents

Source documents provide evidence for the existence of the patient and substantiate the integrity of the data collected. Source documents are filed at the investigator's site. Data entered in the eCRFs that are transcribed from source documents must be consistent with the source documents or the discrepancies must be explained. The investigator may need to request previous medical records or transfer records, current medical records must be available.

9.10.2.2 Direct access to source data and documents

The investigator / institution will permit study-related monitoring, audits, Institutional Review Board (IRB) / Independent Ethics Committee (IEC) review and regulatory inspection, providing direct access to all related source data / documents. eCRFs and all source documents, including progress notes and copies of laboratory and medical test results must be available at all times for review by the sponsor's clinical study monitor, auditor and inspection by health authorities (e.g. Food and Drug Administration (FDA)). The CRA / on site monitor and auditor may review all eCRFs, and written informed consents. The accuracy of the data will be verified by reviewing the documents described in Section 9.10.2.1.

9.10.2.3 Storage of records

Study Site: The site must retain the source documents and essential documents for a period defined by regulations and the site's contract with the sponsor.

Sponsor: The sponsor must retain the essential documents according to the sponsor's SOP.

9.10.3 Statement of confidentiality

Individual patient medical information obtained as a result of this study is considered confidential and disclosure to third parties is prohibited with the exceptions noted below. Patient confidentiality will be ensured by using patient identification code numbers.

Data generated as a result of the study need to be available for inspection on request by the participating investigators, the sponsor's representatives, by the IRB / IEC and the regulatory authorities.

9.10.4 Patient completion

The collection of the data of patients will continue until end of data collection or withdrawal of consent which occurs first.

At the earliest of the above criteria, the Patient Completion information should be completed in the eCRF.

9.10.5 Completion of study

The end of the study will occur when the end of data collection of the last patient's data. No further data will be collected afterwards.

When the study is completed, the investigator should inform the head of the study site of the completion in writing, and the head of study site should promptly inform IRB and sponsor of the completion in writing (For Japan).

The EC/Competent Authority (CA) in each participating country, as required, needs to be notified about the end of the study or early termination of the study.

9.10.6 Protocol Violations

There are no protocol waivers. All protocol violations must be reported to the sponsor immediately.

9.10.7 Compensation available to the patient in the event of study related injury

In the event of health injury associated with marketed product in routine medical practice, the sponsor is not responsible for compensation.

